- Aspartate transaminase (AST) <  $2.5 \times \text{ULN}$ , except for patients with liver metastasis, who are only included if the AST is <  $5 \times \text{ULN}$
- Alanine transaminase (ALT) <  $2.5 \times \text{ULN}$ , except for patients with liver metastasis, who are only included if the ALT is <  $5 \times \text{ULN}$
- Patient must have the following laboratory values within normal limits or corrected to within normal limits with supplements before the first dose of study medication:
  - Sodium
  - Potassium
  - Magnesium
  - Total Calcium (corrected for serum albumin)

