14. Patient has impairment of gastrointestinal (GI) function or GI disease that may significantly alter the absorption of the study drugs (e.g., ulcerative diseases, uncontrolled nausea, vomiting, diarrhea, malabsorption syndrome, or small bowel resection).
15. Patient has a known history of HIV infection (testing not mandatory)
16. Patient has any other concurrent severe and/or uncontrolled medical condition that would, in the investigator's judgment, cause unacceptable safety risks, contraindicate patient participation in the clinical study or compromise compliance with the protocol: (e.g. chronic pancreatitis, chronic active hepatitis, active untreated or uncontrolled fungal, bacterial or viral infections, etc.)
17. [Retired from protocol version 0.0]
- 17a. Clinically significant, uncontrolled heart disease and/or cardiac repolarization abnormality including any of the following:
  - History of angina pectoris, symptomatic pericarditis, or coronary artery bypass graft (CABG), myocardial infarction within 6 months prior to study entry
  - Documented cardiomyopathy
  - Left Ventricular Ejection Fraction (LVEF) < 50% as determined by Multiple Gated acquisition (MUGA) scan or echocardiogram (ECHO)
  - Long QT syndrome or family history of idiopathic sudden death or congenital long QT syndrome, or any of the following:
    - Risk factors for Torsades de Pointe (TdP) including uncorrected hypokalemia or hypomagnesemia, history of cardiac failure, or history of clinically significant/symptomatic bradycardia
    - Concomitant medication(s) with a known risk to prolong the QT interval and/or known to cause Torsades de Pointe that cannot be discontinued or replaced by safe alternative medication (e.g. within 5 half-lives or 7 days prior to starting study drug)
    - Inability to determine the QTcF interval
  - Clinically significant cardiac arrhythmias including but not limited to (e.g., ventricular tachycardia), complete left bundle branch block, high-grade AV block (e.g., bifascicular block, Mobitz type II and third degree AV block)
  - Systolic Blood Pressure (SBP) >160 mmHg or <90 mmHg
  - Bradycardia (heart rate < 50 bpm at rest), by ECG (mean of triplicate) and pulse.
  - Tachycardia (heart rate > 90 bpm at rest), by ECG (mean of triplicate) and pulse.

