## 7 Visit schedule and assessments

### 7.1 Study flow and visit schedule

[Table 7-1a](#) and [Table 7-1b](#) list all of the assessments and indicates with an “X” the visits when they are performed. All data obtained from these assessments must be supported in the patient’s source documentation. The table indicates which assessments produce data to be entered into the database (D) or remain in source documents only (S) (“Category” column).

The following CRF(s) will be used as source document(s): local lab results.

Allowed visit windows are specified as follows:

- Screening assessments, apart from those listed below, must occur within 28 days of the randomization as per [Table 7-1a](#).
- Vital signs, physical exam, ECOG performance status, required labs, physical exam should be performed within 7 days of randomization.  
Note: If the physical examination was performed  $\leq 7$  days prior to the first dose of ribociclib/placebo, then they do not need to be repeated on Cycle 1 Day 1.
- In order for an accurate evaluation of baseline QTc, a total of three 12-lead ECGs will be performed at screening between -7 and -1 day.
- Randomization and Cycle 1 Day 1 should preferably occur on the same day. A maximum of a 3 days window between randomization and Cycle 1 Day 1 visit is permitted.
- For all visits (including PK visits C1D15, C2D1 and C2D15), a general  $\pm 3$  days visit window is permitted on assessments to take into account scheduling over public holidays, if not explicitly specified otherwise.
- For PK sampling, the samples may be obtained within the time window specified in [Table 7-6](#) and [Table 7-7](#).

- Radiological and patient reported outcome assessments must be performed as outlined in [Table 7-1a](#). A visit window of  $\pm 7$  days is allowed. (The whole body bone scan should be performed within 42 days or 6 weeks prior to randomization).
- Any screening assessments required within -7 to -1 days must be repeated if Cycle 1 Day 1 visit is delayed more than 7 days after randomization visit. Every effort should be made to follow the schedule outlined in [Table 7-1a](#).

Patients on placebo+fulvestrant that elect to transition to LEE011+fulvestrant arm or patient who continue with their current treatment (i.e. fulvestrant alone), should have safety assessments as per [Table 7-1a](#) and [Table 7-1b](#). Tumor assessments will continue as clinically indicated as described in [Section 7](#) (see [Table 7-1b](#)).

[figure not shown]

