The assessment schedule for patients who will cross-over is presented in [Table 7-1b](#). Consult [Table 6-4](#), [Table 6-5](#) and [Table 6-6](#) for monitoring frequency in cases of hematologic toxicity, liver function abnormalities or QT prolongation respectively.

Instructions for patients electing to cross-over from placebo to LEE011 at the next scheduled visit:

- All patients commencing LEE011 after cross-over from placebo will need to have hematology, electrolytes and biochemistry tests performed on cross over Cycle 1 Day 1, Cycle 1 Day 15, Cycle 2 Day 1, at the beginning of cycles 3 to 6, then as clinically indicated, but not less frequently than every 12 weeks.
- Patients must have ECG for QT assessment on the first day **before** the administration of LEE011. **LEE011 should be initiated only in patients with QTcF values <450 msec.** ECGs should be repeated on cross-over Cycle 1 Day 15, Cycle 2 Day 1, Day 15 and then as clinically indicated.

**Table 7-1a Visit evaluation schedule - Patients that, after protocol amendment 4, continue with their originally randomized study treatment**

Visit name	Category	Reference to protocol section	Screening phase		Treatment phase						Post treatment follow-up phase			Survival phase
			-28 to -1	-7 to -1	Cycle 1	Cycle 2	Cycle 3	Subsequent cycles	End of study treatment (EOT)	Safety follow-up	Efficacy follow-up	End of post-treatment follow-up	Survival follow-up	
Study days			-28 to -1	-7 to -1	1	15	1	15	1	1	Within 15 days from last dose	Last dose + 30 days	Every 8 weeks (if applicable)	Every 12 weeks
Screening														
Study Informed Consent	D	7.1.1	x											
IRT Screening (after ICF signature)	S	7.1.1	x											
Disposition Assessment														
End of Phase Disposition	D			x							x			x
Patient history														
Demography	D	7.1.1.3	x											
Inclusion/exclusion criteria	D	7.1.1.3		x										
Medical history and current medical conditions	D	7.1.1.3	x											
ER and PgR status	D	7.1.1.3	x											

[figure not shown]

Visit name	Category	Reference to protocol section	Screening phase		Treatment phase						Post treatment follow-up phase			Survival phase	
			Screening	Cycle 1	Cycle 2	Cycle 3	Subsequent cycles	End of study treatment (EOT)	Safety follow-up	Efficacy follow-up	End of post-treatment follow-up	Survival follow-up			
Study days			-28 to -1	-7 to -1	1	15	1	15	1	1	Within 15 days from last dose	Last dose + 30 days	Every 8 weeks (if applicable)		Every 12 weeks

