HER2 status	D	7.1.1.3	x												
Diagnosis and extent of cancer	D	7.1.1.3	x												
Prior antineoplastic therapy	D	7.1.1.3	x												
Prior / concomitant medications	D	7.1.1.3	Continuous – up to 30 days after last dose												
Randomization															
Eligibility checklist (within IRT)	S	7.1.1			x										
IRT - Randomization	D	7.1.1			x										
IRT - study drug administration	S	7.1.1			x		x		x	x	x				
Physical examination															
Physical examination	S	7.2.2.1		x			x		x	Every third cycle	x				
Performance status	D	7.2.2.4		x	x		x		x	Every third cycle	x				
Height	D	7.2.2.3	x												
Weight	D	7.2.2.3	x		x		x		x	x	x				

[figure not shown]
Visit name	Category	Reference to protocol section	Screening phase		Treatment phase						Post treatment follow-up phase			Survival phase	
			Screening	Cycle 1	Cycle 2	Cycle 3	Subsequent cycles	End of study treatment (EOT)	Safety follow-up	Efficacy follow-up	End of post-treatment follow-up	Survival follow-up			
Study days			-28 to -1	-7 to -1	1	15	1	15	1	1	Within 15 days from last dose	Last dose + 30 days	Every 8 weeks (if applicable)		Every 12 weeks
Vital signs	D	7.2.2.2		x	x	x	x		x	Every third cycle	x				
Laboratory assessments															
Hematology	D	7.2.2.5.1		x		x	x		x	Every third cycle	x				
Chemistry with fasting glucose	D	7.2.2.5.2		x		x	x		x	Every third cycle	x				
Fasting Lipid Panel	D	7.2.2.5.3		x					x		x				
Coagulation	D	7.2.2.5.4		x	As clinically indicated						x				
Urinalysis	D	7.2.2.5.5		x			x		x		x				

[figure not shown]
[figure not shown]
Visit name	Category	Reference to protocol section	Screening phase		Treatment phase						Post treatment follow-up phase			Survival phase	
			Screening	Cycle 1	Cycle 2	Cycle 3	Subsequent cycles	End of study treatment (EOT)	Safety follow-up	Efficacy follow-up	End of post-treatment follow-up	Survival follow-up			
Study days			-28 to -1	-7 to -1	1	15	1	15	1	1	Within 15 days from last dose	Last dose + 30 days	Every 8 weeks (if applicable)		Every 12 weeks
Tumor assessment															

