Hematology	D	7.2.2.5.1	x	x	x		x	Every 3 rd cycle	x					
Biochemistry (including fasting glucose)	D	7.2.2.5.2	x	x	x		x	Every 3 rd cycle	x					
Fasting Lipid Panel	D	7.2.2.5.3	x						x					
Coagulation	D	7.2.2.5.4	As clinically indicated							x				
Urinalysis	D	7.2.2.5.5	As clinically indicated							x				
Tumor Assessments														
Tumor Evaluation (RECIST 1.1)	D	7.2.1	As clinically indicated											
Fluid/Tissue collection results (if available)	D	7.2.1	As clinically indicated until disease progression											
Whole body bone scan	D	7.2.1	As clinically indicated											
Safety														
Triplicate ECG (standard 12-lead)	D	7.2.2.6.1	x	x	x	x	As clinically indicated		x					
ECHO or MUGA with EF	D	7.2.2.6.2	As clinically indicated											

Visit name	Category	Reference to Protocol Section	Treatment Phase - only applies to cross-over patients for cross over treatment cycles					Post treatment follow-up phase			Survival phase			
			Cross over Cycle 1	Cross over Cycle 2	Cross over Cycles 3 to 6	All subsequent Cross over cycles	End of study treatment (EOT)	Safety follow-up	Efficacy follow-up	End of post-treatment follow-up	Survival follow-up			
Study days			1	15	1	15	1	1	Within 15 days from last dose	Last dose + 30 days	Every 8 weeks (if applicable)		Every 12 weeks	
Concomitant medications/procedures	D	6.6	Continuous - up to 30 days after last dose											
Adverse events	D	8.1	Continuous – up to 30 days after last dose											
Study Drug administration														
Fulvestrant	D	6.1.1	x		x		x	Day 1 of each cycle						
Ribociclib (LEE011)	D	6.1.1	Day 1 to Day 21 daily, Day 22 to Day 28 off											
Disposition Assessment														
End of Phase Disposition									x				x	
Discontinuation														
IRT – Discontinuation	S	7.1.3							x					

Visit name	Category	Reference to Protocol Section	Treatment Phase - only applies to cross-over patients for cross over treatment cycles						Post treatment follow-up phase			Survival phase		
			Cross over Cycle 1		Cross over Cycle 2		Cross over Cycles 3 to 6	All subsequent Cross over cycles	End of study treatment (EOT)	Safety follow-up	Efficacy follow-up	End of post-treatment follow-up	Survival follow-up	
Study days			1	15	1	15	1	1	Within 15 days from last dose	Last dose + 30 days	Every 8 weeks (if applicable)		Every 12 weeks	
Survival follow-up	D	7.1.7												x

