**Table 7-5b Local ECG collection plan – for crossover patients**

Patients	Cross Over Cycle	Day / time	ECG type
All	1	Day 1 / Pre-dose 	Triplicate 12 Lead
All	1	Day 15 / anytime	Triplicate 12 Lead
All	2	Day 1 / anytime	Triplicate 12 Lead
All	2	Day 15 / anytime	Triplicate 12 Lead
All	All other cycles	As clinically indicated	Triplicate 12 Lead
All	EOT	Anytime	Triplicate 12 Lead
All	Unscheduled ECG	Anytime	Triplicate 12 Lead
 The exact date and time of dosing must be recorded on the appropriate eCRF			

[figure not shown]
Patients in the placebo arm who elect to transition from placebo to LEE011 must have ECG for QT assessment on the first day **before** the administration of LEE011. **LEE011 should be initiated only in patients with QTcF values <450 msec.** ECGs should be repeated on cross-over Cycle 1 Day 15, Cycle 2 Day 1, Day 15 and then as clinically indicated as per [Table 7-5b](#).

In order for an accurate evaluation of baseline QTcF, a total of three 12-lead ECGs will be performed within 7 days prior to randomization (at screening between Day -7 and Day -1).

**Note:** In order to ensure ECG evaluation is received from the central laboratory for eligibility assessment, it is advisable to perform the ECG at least 24 hours prior the scheduled randomization date.

If a QTcF value of  $\geq$  481 ms is observed in a single ECG or as the average (when collected as a triplicate) at any time after randomization, study treatment must be interrupted, repeat ECG(s) and follow management guidelines detailed in [Table 6-6](#).

An unscheduled ECG may be repeated at the discretion of the investigator at any time during the study and as clinically indicated. Unscheduled ECGs with clinically significant findings

should be collected in triplicate. Additionally, a local cardiologist may be consulted at any time during the study at the discretion of the investigator. If an unscheduled ECG is performed at an external medical facility, a copy of the ECG should be obtained and forwarded to the ECG central laboratory, and a copy kept in the source documents at the study site. Centrally reviewed ECG findings should be documented on the ECG CRF page.

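### At cross-over, starting ribociclib depends on a pre-dose QTcF but not on a reviewed electrolyte result: a minor safety gap that is cheap to close

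*Protocol*

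**What the plan says.** **Cross-over, ECG.** Section 7.1 requires an ECG on the first day, before LEE011 (ribociclib), and sets a limit: "LEE011 should be initiated only in patients with QTcF values <450 msec". Section 7.2.2.6.1 repeats both ("Patients in the placebo arm who elect to transition from placebo to LEE011 must have ECG for QT assessment on the first day"), and Table 7-5b labels that ECG as pre-dose.

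**Cross-over, laboratory.** The preceding bullet in Section 7.1 says these patients "will need to have hematology, electrolytes and biochemistry tests performed on cross over Cycle 1 Day 1", with further test days after that. It does not place the sample before the dose, set a limit, describe correction, or call for review of the result. Table 7-1b puts a plain x for biochemistry at cross-over Cycle 1 Day 1. Sections 4.1.2, 4.3, 6.1 and 6.3.2, which also describe cross-over, add no electrolyte condition.

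**Original entry.** Item 8a in Section 5.2 requires sodium, potassium, magnesium and albumin-corrected calcium to be "within normal limits or corrected to within normal limits with supplements before the first dose of study medication". Item 17a in Section 5.3 lists "Risk factors for Torsades de Pointe (TdP) including uncorrected hypokalemia or hypomagnesemia".

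**The concern.** The protocol treats two things as preconditions for safely starting a QT-prolonging drug: an acceptable QTcF, and electrolytes that are normal or have been corrected. At cross-over it renews the first and not the second. Placebo patients satisfied item 8a years earlier, before a first dose that contained no ribociclib.

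The ECG limit does not stand in for the electrolyte check. It is a reading without ribociclib on board, so a patient can pass it with low potassium or magnesium. The Amendment 3 rationale states that ribociclib prolongs QT in a concentration-dependent way. Section 1.2.1.2.1 reports that 4 patients (5.4%) at 600 mg in the phase I study had asymptomatic prolongation to 500 ms or more. The stake is patient safety in a small group, not the trial's conclusions.

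**Working it through.** The main check is a comparison of texts. The protocol states no figure on this point to reproduce.

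**1. Entry against cross-over**

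| Condition before first dose | Original entry | Cross-over to ribociclib |
|---|---|---|
| QTcF | Exclusion above 450 msec (item 17a) | Pre-dose ECG, below 450 msec (7.1, 7.2.2.6.1, Table 7-5b) |
| Sodium, potassium, magnesium, corrected calcium | Normal or corrected (item 8a) | Sample on Day 1; no limit, correction step or review before dosing (7.1, Table 7-1b) |

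**2. Does other text supply the missing condition?**

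- Table 6-6 orders an electrolyte check, interruption and correction, but as management of QTcF prolongation, with grades starting at 450 ms. A patient who passes the cross-over limit does not trigger it.
- Section 6.5.1.2.3 says to consider electrolyte testing for adverse reactions; where values are abnormal, it instructs interruption, correction and repeat testing until normal. Section 8.1.1 counts a laboratory abnormality that requires therapy as an adverse event, so a Day 1 value needing supplements plausibly falls under this instruction. It acts once the result is known, which may be after the first dose.
- Section 7.2.2.5 sends scheduled chemistry to the central laboratory, makes the investigator responsible for reviewing all reports, and permits local testing without requiring it. No turnaround time is given.
- Sections 6.1.1.1 (supervised dosing on visit days) and 6.1.1.2 (overnight fast for fasting glucose) make a pre-dose draw likely. Neither requires the result.

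**3. Length of the exposed period.** Section 1.2.1.2.1 says QT changes become evident by Day 8 and later. ECG and chemistry are repeated on cross-over Cycle 1 Day 15. The unprotected period is therefore mainly from the first dose until the Day 1 result is acted on.

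**4. Age of the last known result at first dose**

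- Entry: Table 7-1a places "Chemistry with fasting glucose" in the Day -7 to -1 screening column, with none on Cycle 1 Day 1, and Section 7.1 states that "A maximum of a 3 days window between randomization and Cycle 1 Day 1 visit is permitted". So 7 + 3 = 10 days at most within the permitted windows.
- Cross-over, if the Day 1 result is not back: with chemistry every third cycle (Table 7-1a), 3 × 28 = 84 days. This holds only if that schedule was already in force. Table 7-1a is the Amendment 4 table, and the schedule before it is not shown.

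**5. Size of the group (assumption).** The documents do not say how many placebo patients were still on treatment. Inputs:

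- 727 randomised 2:1, so 727/3 ≈ 242 on placebo.
- Enrolment from June 2015 to 14 June 2016; Amendment 4 dated 29 January 2020. Time since randomisation is about 43.5 to 55.5 months (taking mid-June 2015 as the start).
- Section 10.8: 40% first line and 60% second line; second-line median m2 = 6.5 months; first-line median m1 taken as 18 months from a cited range of 8 to 23.

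Proportion progression-free, assuming exponential times: S(t) = 0.4·exp(−ln2·t/m1) + 0.6·exp(−ln2·t/m2).

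| m1 (months) | t = 43.5 | t = 55.5 |
|---|---|---|
| 8 | 1.50% (3.6 patients) | 0.49% (1.2) |
| 18 | 8.07% (19.6) | 4.88% (11.8) |
| 23 | 11.36% (27.5) | 7.67% (18.6) |

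That is about 1 to 28 patients, or 12 to 20 on the plan's 18-month value. With Section 10.8's lower second-line median of 4.8 months, the range is about 1 to 26 (0.8 to 26.4).

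**The case against.** The strongest case against is that existing safeguards already do most of the work. Electrolytes are mandatory on Day 1, the investigator must review every report, Section 6.5.1.2.3 calls for interruption and correction when values are abnormal, and QT effects take about a week to appear. A Day 1 sample, even a central one, is well placed to be acted on in time. This stands, and it is why the point is minor. It does not remove the gap: none of these provisions makes the first dose wait for the result.

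Three further objections also stand in part.

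- Item 8a speaks of study medication, so extending it to first ribociclib exposure is a reading of its purpose. The reading is reasonable, because Amendment 4 sets a fresh QTcF condition for the same patients.
- The plain x in Table 7-1b proves nothing about intended order, because the ECG row there also has a plain x. The difference rests on Section 7.1 and Table 7-5b.
- The head count models progression-free survival, not time on treatment. Its 8-month lower end matches the 250 mg fulvestrant result in Section 1.2.2 (8.2 months), whereas this trial uses 500 mg.

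A reader might infer more: that the protocol contradicts itself, that it lets patients continue on ribociclib with uncorrected electrolytes, or that patients will be started on a result 84 days old while randomised patients had one at most 10 days old. The documents do not support these. The cross-over text is silent rather than inconsistent, known abnormalities have a correction route, and the 84 days depends on an unseen earlier schedule and on the Day 1 result being unavailable.

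**Conclusion.** The omission is real but minor. The protocol re-applies the QTcF condition at first ribociclib exposure and does not re-apply the electrolyte condition, so a patient with an acceptable ECG and uncorrected low potassium or magnesium may take the first doses before the abnormality is known.

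The group is small. The estimate of about 1 to 28 is a working assumption, and the number who cross over may be lower, because cross-over is optional, needs consent and local approval of the amendment, and is open only to patients still on study treatment. The number with abnormal electrolytes cannot be derived. No formal efficacy test is affected: PFS and OS had both been declared significant before cross-over opened.

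This is a cheap improvement to patient safety. It should not be read as evidence that patients were harmed or that the trial's results are in doubt.

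**What to change.** Add to the first cross-over bullet in Section 7.1:

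*Electrolytes must be sampled (central or local laboratory) within the 3 days before the first LEE011 dose, or on the same day before that dose. LEE011 should be started only once potassium, magnesium and albumin-corrected calcium (and sodium, for consistency with item 8a) have been reviewed and are in range, or have been brought into range with supplements.*

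Mark biochemistry at cross-over Cycle 1 Day 1 as pre-dose in Table 7-1b. Leave haematology, liver tests and later test days as they are.

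The time limit covers local as well as central samples, so an old local result does not qualify. Naming the local laboratory also avoids doubt, because Section 7.2.2.5 restricts eligibility decisions to central results.

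**Cost.** Two sentences and one table label. There are no new analytes: all four are in the Table 7-4 panel. Some patients may need a local run (with a parallel central sample where possible), an earlier draw that could mean an extra visit, or a retest after correction, and may start LEE011 a few days later. Sodium has the weakest QT rationale, since neither item 17a nor the on-treatment electrolyte checks name it. If delay for mild hyponatraemia is unwelcome, it is the one to drop.
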